#### 5.4 Non-exercise cardiorespiratory fitness estimate

At baseline, participants will be asked to wear an accelerometer and have their cardiorespiratory fitness (CRF) estimated. The assessment of cardiorespiratory fitness (CRF) is associated with burdens of time, cost, risk and resources. To address this concern, we will take advantage of a non-exercise estimate of CRF. CRF will be estimated by a method developed by [Jurca et al. \(2005\)](#) [18] and validated by [Mailey et al. \(2010\)](#) [26]. The estimation uses a regression equation that includes age, sex, body mass index, resting heart rate, and self-reported physical activity. We will obtain a non-exercise CRF estimation before and four weeks after the intervention. To perform the CRF estimation, we will collect the resting heart rate after participants have rested quietly for ten minutes.

### 5.5 Neuropsychological Assessment

If participants pass this second screening, they will complete neuropsychological and behavioural inventories. We expect testing to take about 3 hours and will administer the assessments with breaks every ~40 minutes to reduce fatigue. They will complete behavioural inventories that capture individual differences in traits potentially predicting responsiveness to the intervention. These measures (listed in the attached spreadsheet) include validated questionnaires to assess factors like motivation for physical activity, self-efficacy for exercise, self-efficacy for walking, barriers to exercise, mood, conscientiousness and grit, growth mindset, loneliness, future time perspective, and purpose in life. Participants' educational attainment and total personal income levels will also be collected to create a measure of socioeconomic status, as described by [Hartanto et al. \(2019\)](#) [19]. These questionnaires will be administered through REDCap, a "secure, HIPAA-compliant, web-based application... housed in a secure local data center, behind the Tufts Medical Center firewall, and all web-based information is encrypted" ([tuftsctsi.org/research-services/informatics/redcap-research-electronic-data-capture/](http://tuftsctsi.org/research-services/informatics/redcap-research-electronic-data-capture/)).

Participants will also complete a cognitive battery (also listed in the attached spreadsheet) that examines important cognitive constructs that have been associated with changes in physical activity and aging including executive function (i.e., the Brief Test of Adult Cognition by Telephone [BTACT]), working memory (n-back, WAIS-IV Digit Span Forwards and Backwards), sustained attention and motor speed (WAIS-IV Coding test, simple reaction time), verbal fluency (Category and Phonemic Fluency tests), and episodic memory (Hopkins Verbal Learning Test – Revised (HVLT-R). Neuropsychological measures will be administered remotely via telephone encrypted videoconferencing (using HIPAA compliant Zoom software) and secure, coded platforms such as Test My Brain ([testmybrain.org](http://testmybrain.org)). Additional paradigms are described below:

The *Intrinsic Motivation Effort Expenditure for Rewards Task* (EEfRT), captures the construct of Reward Valuation and Effort. This multi-trial computerized task presents participants with a (variable) level of reward and a (variable) amount of work (effort) to win that reward. For each trial, the participant must accept or reject the proposal based on whether they think the reward is worth the effort. If they accept the trial, they have a 1/3 chance of then being asked to perform that work. The "work" is fast key presses on the left and right arrow keys, using the right-hand index and middle fingers. The amount of work is communicated using a vertical rectangle with a horizontal line through it at different heights; the higher the line, the more key presses are required. Participants are given visual feedback during the trial as the line is moved to the bottom and is progressively raised with each button press, with the goal of

raising the line up to its original height for that trial. Rewards come from three domains: monetary rewards (hypothetical money), social rewards (hypothetical time with loved ones), and intrinsic rewards from curiosity (the answers to trivia questions). There are 6 “levels” of reward in each of the three domains, and 5 levels of work.

The *Option Generation Task* [22] measures participants’ fluency and ability to generate options for future behaviour. In each trial, the experimenter will present the participant with a hypothetical “open” (e.g., It’s a rainy and cold Sunday. What could you do?) or “problem-solving” situations (e.g., You are in a foreign city and you are lost. What could you do?).

The participant will be given 2 minutes to generate options for action. They will be encouraged to describe each option briefly, mainly using keywords.

The *Delay Discounting Task* is a measure of temporal discounting; the tendency for people to prefer smaller, immediate monetary rewards over larger, delayed rewards. Participants will respond to a series of 27 questions that ask them to choose between a smaller, immediate reward (e.g., \$25 today) versus a larger, later reward (e.g., \$35 in 25 days). The 27 items are divided into three groups according to the size of the larger amount (small, medium, or large). Modeling techniques are used to fit the function that relates time to discounting. The main dependent measure of interest is the steepness of the discounting curve such that a more steeply declining curve represents a tendency to devalue rewards as they become more temporally remote (Science of Behavior Change, Columbia University).

The *Future Time Perspective Task* [24, 25] assesses the length of individuals’ views of the future, where more limited views of the future have been linked with pathological impulsive behavior like drug use. Participants will be asked to generate a list of five future life events and respond orally, without a time limit. After the events are generated, the experimenter will ask the participant to estimate how far into the future each event might occur. The two dependent measures for this task are the ‘extension’, which is the maximum length of time generated by each subject, and the mean future time period for all five items.

In the *simple reaction time task*, the participant will be presented with a blank white screen and asked to press a button as quickly as possible each time a large, black “X” appears. The “X” will always appear in the same spot in the center of the screen. This measures the participant’s reaction times.

In summary, in order to understand the variability in participants’ responses to persuasive messaging, we will explore a rich dataset of individual differences across behavioural traits and cognitive, structural, and functional brain measures. All brain imaging and biomarkers have been already collected under the auspices of the ongoing PREVENT-AD study, of which the PI, [name], is a formal collaborator. Some of these tests will be administered verbally by adapting in-person, pen and paper versions to phone calls or video conferencing formats. Certain phone-based tasks require researchers to collect audio recordings of participant responses for timing and other scoring purposes. Online replacement tests will be administered using TestMyBrain.org and Pavlovia.org.

TestMyBrain was developed by [name] and colleagues in 2008 and is updated continuously. TMB provides online alternatives to classic pen-and-paper neuropsychological assessment tools and has normative data from thousands of online test subjects aged 12 to 90. TMB only provides tests that have been validated online and shown to be comparable to hard-copy versions. The TMB Neuropsychology Toolkit follows HIPAA regulations and does not collect personal identifiable data or demographic information. They retain test performance data for quality assurance and temporarily store access information (IP address, access URL, timestamp, and user agent) for 14 days to help prevent or identify security breaches or other fraudulent behaviour.

Pavlovia was created by John Pierce and colleagues at the University of Nottingham and is now run by Open Science Tools LTD. It is fully GDPR, or General Data Protection Regulation, compliant. The GDPR concerns data protection and privacy in the European Union and the European Economic Area. Source: <https://pavlovia.org/docs/home/ethics>

Participants will be assessed remotely with accelerometers and have their cardiorespiratory status estimated. The estimation uses a regression equation that includes age, sex, body mass index, and resting heart rate. We will obtain a non-exercise CRF estimation before and after the four-week intervention. To perform the CRF estimation, which will be remote, we will ask participants to report their supine resting heart rate after they have rested quietly for ten minutes. Participants will also complete a remote physical assessment focused on their basic walking speed, their ability to transition repeatedly from sitting to standing, and their balance.

Accelerometers, chargers, and related materials will be sent to participants through the mail after the consent meeting and will be returned after the end of the first study period. Accelerometry data will be recorded during wakefulness and sleep, with the exception of bathing or swimming, for the week between T1 and T2 (before the intervention begins; i.e., baseline), for two separate weeks during the 4-week intervention (with additional days during this timeframe for any participant who does not wear the devices consistently during the original period). This will characterize changes in physical activity from baseline and maintenance. It will be assessed using two accelerometers worn simultaneously. The first is a wrist-worn tri-axial accelerometer (ActiGraph GT3X Link, Pensacola, FL). This accelerometry data will be downloaded in 60-second epochs (ActiLife software, ActiGraph, Pensacola, FL) and will be screened for wear time using standard methods [26]. The second device is a tri-axial accelerometer and inclinometer and will be worn on the thigh using an adhesive.

Physical activity will be measured with an ActiGraph accelerometer model GT9X Link (ActiGraph LLC, Pensacola, FL). The ActiGraph GT9X Link is a small (3.5 x 3.5 x 1 cm) and light (14 g) device that measures acceleration in three planes: vertical, anteroposterior and mediolateral. Participants will wear the device on their wrists 24 hours a day to improve compliance. The 24-hour protocol has resulted in greater compliance over waking time wear protocol [27]. Participants will be instructed to take the device off for swimming, showering and bathing. Data from this device will be synced with the CentrePoint app (HIPAA compliant, also through ActiGraph) on the participant's phone or computer. Raw data will be reduced and processed using ActiLife software (<http://www.actigraphcorp.com>). Participants will fill in sleep and activity logs.

The physical assessment administered at T1, T3, and T4 will involve the 2-minute walking test adapted from the NIH Motor Battery, a 20-second sitting-to-standing test (also used in the CDC's STEADI toolbox), and observations of balance while doing everyday activities like putting on shoes. We will record these physical assessments using Zoom. These are sensitive measures often used with older adults that reflect their fitness, especially their lower-body strength. Choosing these sensitive measures makes it more likely that we will be able to detect fitness changes post-test if the intervention results in the behaviour changes we expect.

[figure not shown]

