**3.8.3.c Donation to the Alzheimer's Society**

Based on the participant's physical activity performance and their pre-set goals (# of steps increase or amount of time increase being active) during the 4-week intervention period, a maximum amount of 3.00\$ per week would be saved to be donated to the Alzheimer's society at the end of the intervention (up to 18.00\$ for the whole intervention).

Week	Donation
Week 1	Up to 3.00\$
Week 2	Up to 3.00\$
Week 3	Up to 3.00\$
Week 4	Up to 3.00\$
Total Amount	Up to 12\$

The 3.00\$ will be saved for donation if the participant achieves 100% of their goal on a given week.

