## 5 Intervention

### 5.1 Study timeline

An illustration of the study timeline can be seen in Figure 1. Informed consent is obtained at the initial video-conferenced meeting. Each participant undergoes a baseline session (T1) one week before the beginning of the intervention. As a baseline, participants wear a wrist-worn accelerometer on their non-dominant hand to assess physical activity (see physical activity monitoring). Physical assessments will be administered at baseline. The accelerometer is worn for a week. The intervention lasts 4 weeks, during which participants receive daily intervention messages via email or phone. Participants are fitted with the accelerometers again for a one-week mid-intervention period. The post-intervention session (T3) is scheduled at the beginning of the last intervention week (week 4), during which participants repeat psychosocial surveys and neuropsychological tests. All sessions are administered remotely through online surveys and computer tasks (please see timeline document).

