### 5.3 Daily messaging

[figure not shown]
The 4-week intervention consists of daily self-transcendence messages via email using the encrypted online software oTree, an open-source platform for implementing messaging surveys, which allows for accessibility via desktop or smartphone [17]. Unique, coded links are assigned to each participant at enrollment. Participants will be requested to: "For the next 30 seconds contemplate the warm feelings you have towards a loved one as vividly as you can. Think about a situation where the following wish comes true for your loved one: May you be well". Examples of daily self-transcendence prompts rotate among:

- May you be well
- May you be happy
- May you be safe
- May you be at ease
- May you be healthy

- May you be peaceful
- May you find wholeness
- May you be joyful

Each day if they reach their physical activity goal, the main participants will receive messages from a pre-set list of messages composed at the consent session by their study partners (see Annex A – time capsule). The participant will then rate their mood and confidence in implementing the health tips, the goal of which is to examine the changing in well-being and self-efficacy of physical activity throughout the intervention. During weeks 2 and 4, they also receive daily reminders to continue wearing their accelerometer. This daily message survey setup is displayed in Figure 2. The researcher's contact information is displayed on each survey page to enhance compliance. Participants' responses are tracked and those that do not complete the survey by a specified time of day are contacted the following day by research assistants to prevent technical failures.

In addition to self-transcendence health messages, participants in the intervention arm will receive feedback about their daily physical activity using the CentrePoint encrypted software package from Actigraph (<https://actigraphcorp.com/cdh/>). The CentrePoint data hub is a home-based communication gateway that securely transmits data captured by the Actigraph activity monitors to provide near real-time feedback to participants about daily physical activity.

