#### 6b Data analysis

Outcome measures outside of the neuropsychological assessment battery are as follows:

Outcome measure	Type	Timeframe	Brief description
Total step count (average steps/day)	Primary	Week 0 (baseline); Week 2; Week 4.	This metric quantifies the change in the average number of steps taken each day, from the baseline, Week 2, and Week 4. It is a marker of change in habitual ambulatory activity.
Sedentary behavior (average min/day)	Primary	Week 0 (baseline); Week 2; Week 4.	This metric quantifies the change in the average amount of time spent sedentary each day, from the baseline, Week 2, and Week 4.

			2, and Week 4. It is a marker of time spent inactive.
Moderate-vigorous activity (average min/day)	Secondary	Week 0 (baseline); Week 2; Week 4.	This metric quantifies the change in the average amount of time spent engaged in moderate-to-vigorous physical activity each day, from the baseline, Week 2, and Week 4. It is a marker of physical activity.
Walking Cadence	Secondary	Week 0 (baseline); Week 2; Week 4	This metric reflects the participant's average steps per minute. We will examine change from baseline over the course of the intervention.
Walking Bouts	Secondary	Week 0 (baseline); Week 2; Week 4	This measures the number of 'bouts' of physical activity (in our case, steps). We will have two counts: the number of 5+ minute bouts and the number of 10+ minute bouts of walking. We will examine changes from baseline over the course of the intervention.

A spreadsheet holding the list of neuropsychological assessments to be used, with brief descriptions, is attached. They will be administered at T1 (Week 0), T2 (Week 1), and T3 (Week 4).

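### The primary step count appears to come from the wrist monitor whose readings are fed back and rewarded in the intervention arm, and the thigh monitor worn alongside it has no role as a check

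*Protocol*

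**What the plan says.** **Outcome.** The table in Protocol 6b lists average steps per day as a primary outcome, beside sedentary time: "This metric quantifies the change in the average number of steps taken each day". It names no device, wear site or step algorithm. Cadence and walking bouts are secondary.

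**Wrist device.** Section 5.1 has the baseline week recorded at the wrist: "participants wear a wrist-worn accelerometer on their non-dominant hand to assess physical activity". Section 5.5 says "Physical activity will be measured with an ActiGraph accelerometer model GT9X Link", adds "Participants will wear the device on their wrists 24 hours a day to improve compliance", and continues "Data from this device will be synced with the CentrePoint app".

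**Feedback and rewards.** Section 5.3 says "participants in the intervention arm will receive feedback about their daily physical activity using the CentrePoint encrypted software package from Actigraph". The same section sends messages composed by the study partner on days when the activity goal is met. Section 5.6 (Study partner) repeats this, gives the partner feedback on the participant's accelerometer results, and confines the partner to the period in which the participant is in the intervention arm. Section 3.8.3.c ties a weekly donation of up to $3 to "pre-set goals (# of steps increase or amount of time increase being active". Section 3.8.3.d applies the same principle in the cross-over segment to those moving into the intervention.

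**Thigh device.** Section 5.5 also states that two accelerometers are worn at the same time: "The second device is a tri-axial accelerometer and inclinometer and will be worn on the thigh using an adhesive". Neither document assigns this device to an outcome, gives its make or processing, or plans a comparison with the wrist readings.

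**The concern.** A step goal is a sensible part of the intervention. The difficulty comes when the instrument that judges the goal also supplies the primary outcome, and the reward attached to it is in one arm. A wrist sensor records wrist acceleration, so arm movement without walking may be scored as steps. A participant who is shown the reading and rewarded on it has a reason, conscious or not, to move it. Randomisation does not protect against measurement error that the allocated treatment itself creates.

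Such an error would favour the intervention. It would carry into cadence and walking bouts if these come from the same device. Screening for wear time would not reveal it, because the device is being worn, and a larger sample would not remove it. What is at stake is whether a positive step result can be read as more walking. The plan already includes a second device at another body site that could test this, but does not use it.

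**Working it through.** **1. Following the reading through the Protocol**

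| Link | Source | How firm |
|---|---|---|
| Steps per day is primary | 6b | Stated |
| Physical activity is measured at the wrist | 5.1, 5.5 | Stated for physical activity in general; not repeated for the step outcome in 6b |
| Wrist data go to CentrePoint | 5.5 | Stated, not limited by arm |
| CentrePoint feedback to participants | 5.3 | Described for the intervention arm; silent on controls |
| Partner sees accelerometer results | 5.6 (Study partner) | Stated, intervention period only |
| Goal reached earns partner messages | 5.3, 5.6 (Study partner) | Stated; needs a partner, so intervention only. Reading that judges the goal not named |
| Goal reached earns donation | 3.8.3.c, 3.8.3.d | Stated; arm given only for the cross-over. Reading not named |
| Thigh device outside the feedback loop | 5.3, 5.5 | Not stated either way |

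That the wrist reading judges the goals is an inference. Donations run over all four weeks, whereas 5.5 records accelerometry in two separate weeks of the four, so the source is not fully settled.

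**2. The plan's own sample-size figure**

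Inputs from the SAP: difference 10.0%, SD 14.0%, two-sided alpha 0.05, power 80%, 30 per arm.

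- n per arm = 2 × (1.960 + 0.842)² × 14² / 10² = 30.8, so 31 per arm (62 in all).
- Standard error at 30 per arm = 14 × √(2/30) = 3.61. Power = Φ(10/3.61 − 1.960) = 0.790. With the noncentral t it is 0.776.

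The SAP's 60 is reproduced to within rounding.

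**3. Illustration of an artefact in one arm**

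The documents give no rate at which arm movement is scored as steps, so the bias cannot be derived from them. Assume no true effect, an SD of 14.0% for the step outcome, and an inflation of b percentage points in the intervention arm only. The two-sided 5% t-test then rejects with probability P(|T| > t₀.₉₇₅), where T is noncentral t with 2n − 2 degrees of freedom and noncentrality b / (14 × √(2/n)). The divisor is 3.61 at 30 per arm (the SAP's 60) and 2.56 at 60 per arm (the Protocol's 120, allocated 1:1).

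| Assumed b | Share of the 10.0% difference | Noncentrality, n = 30 | Rejects, n = 30 | Noncentrality, n = 60 | Rejects, n = 60 |
|---|---|---|---|---|---|
| 0 | 0% | 0 | 0.050 | 0 | 0.050 |
| 2 | 20% | 0.55 | 0.085 | 0.78 | 0.121 |
| 3 | 30% | 0.83 | 0.129 | 1.17 | 0.214 |
| 5 | 50% | 1.38 | 0.275 | 1.96 | 0.492 |

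The larger sample makes a false positive more likely, because the bias stays while the standard error shrinks.

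Two assumptions carry the table. The range for b has no source in the documents. The SAP attaches its 10.0% and 14.0% to physical activity without naming steps, and the outcomes that 6b expresses as percentages are sedentary or sitting and lying time.

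**The case against.** The strongest reply is that the plan does not say the wrist unit supplies the primary step count. Section 6b names no device, and 5.5 says activity is assessed with both. Section 6b also analyses sitting and lying time, a posture measure, and the only inclinometer described is the one on the thigh, so the sponsor may already intend to use it. This stands as far as it goes: the wrist is the natural reading for steps, not a stated fact. It leaves the source of a primary outcome open, which also needs correcting.

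Second, ordinary wrist error affects both arms and the baseline week as well. Bias arises only if intervention participants move their arms more without walking. The device is on the non-dominant hand, the donation is small and goes to charity, and under the note on blinding in 4.2 participants are not told that the messages are the intervention. This makes a large artefact less likely. It does not remove the incentive, since a participant need not know what the intervention is to want to reach a goal.

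Third, a reader might infer that the thigh monitor is independent of the feedback and that controls see nothing. The documents support neither. Section 5.3 refers to activity monitors in the plural, the make of the thigh device is not given, the CentrePoint sync in 5.5 is not limited by arm, and 4.1 describes controls as having their activity monitored daily. Even if controls see their readings, partner messages and partner feedback remain confined to the intervention.

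Fourth, no passage shows that the thigh device outputs steps or how its wear time is processed, and Section 9 has participants stop using a device that causes discomfort. This stands, and it is why making the thigh device primary cannot be called a required correction.

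**Conclusion.** The point holds as a gap in specification together with a plausible, untested risk of arm-dependent measurement error. On the most natural reading of 5.1 and 5.5, the primary step count is also the rewarded target in the intervention arm, and nothing planned would show whether the two arms are measured alike.

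The size is unknown. The rejection rates of 8.5% to 27.5% at 30 per arm, and 12.1% to 49.2% at 60 per arm, show what an assumed inflation of 2 to 5 points would do with an SD borrowed from the SAP. A reader might take them as this trial's false-positive rate; they are not, and they do not show that the bias exists.

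Nor do the documents support the inference that a positive step result would be uninterpretable. Sedentary time is also primary, though it has the same gap in device assignment, and 5.5 adds activity logs and a 2-minute walking test. The change is worth making because it is cheap and tests the risk directly.

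**What to change.** In Protocol 6b and the SAP:

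- Name the device and the algorithm for each primary outcome, steps per day and sedentary time.
- State whether control participants can see their readings, in CentrePoint or elsewhere.
- State whether the thigh device drives any feedback, message or donation, and which reading judges the goals.
- Provided the thigh device is outside the feedback loop and yields steps, pre-specify a sensitivity analysis of steps per day, cadence and walking bouts from it.
- Under the same condition, report wrist-minus-thigh steps by arm at baseline, week 2 and week 4. A difference that opens in one arm after baseline would be direct evidence of unequal measurement.

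Once these facts are confirmed, the sponsor may choose to make the thigh device the primary source; the documents as they stand do not compel it.

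The cost is wording in both documents and extra processing of data from a device that participants are already due to wear. Some thigh data will be missing if the adhesive is not tolerated. A mixed model copes with that only if the data are missing at random, so the amount missing should be reported by arm.
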